1 DEFINITIONS AND ABBREVIATIONS

Term	Description
ADE	Adverse Device Effect
ADRO	Adaptive Dynamic Range Optimisation
AE	Adverse Event
AMDT	Approved Medical Device on Test
AuSTIN	Australian Speech Test In Noise
BEAM	Adaptive Beamformer
BTE	Behind The Ear
BLE	Bluetooth Low Energy
CER	Clinical Evaluation Report
CI	Cochlear Implant
CIP	Clinical Investigation Plan
CIR	Clinical Investigation Report
CNC	Consonant Nucleus Consonant
CRF	Case Report Form
CRO	Contract Research Organisation
DCF	Data Clarification Form
DD	Device Deficiency
EC	Ethics Committee Synonymous abbreviations/terms include: IRB (Institutional Review Board) IEC (Institutional Ethics Committee or Independent Ethics Committee) HREC (Human Research Ethics Committee)
eCRF	Electronic Case Report Form
EDC	Electronic Data Capture
FF	Forward Focus
GCP	Good Clinical Practices
IB	Investigator's Brochure
ICF	Informed Consent Form
IDMC	Independent Data Monitoring Committee
IMD	Investigational Medical Device
ITT	Intent-To-Treat (ITT) and
NCA	National Competent Authority
NFS	Nucleus Fitting Software
NF	Notch Filter

Clinical Investigation Plan: CLTD5818

Term	Description
OTE	Off-the-Ear
PI	Principal Investigator
PIL	Principal Investigator List
PMS	Post-Market Surveillance
PP	Per Protocol
RF	Radio Frequency
SADE	Serious Adverse Device Effect
SAE	Serious Adverse Event
SAP	Statistical Analysis Plan
SNR-NR	Signal to Noise Ratio- Noise Reduction
SOP	Standard Operating Procedure
SRT	Speech Reception Threshold
SSQ	Speech, Spatial and Qualities
std	Standard directionality
SWN	Speech Weighted Noise
UADE	Unanticipated Adverse Device Effect
USADE	Unanticipated Serious Adverse Device Effect

2 CLINICAL INVESTIGATION SYNOPSIS

Investigation title	A Pre-Marketing, Prospective, Single-Site, Op en-Label, Wi t hin-Subject, Pilot, Interventional Study of Adult Cochlear Implant Speech Perception with the Kanso 2 (CP1150) So und Processor Compared with the Next Generation of Signal Processing Technology
Short title	OPTIMUM Study
Investigation number	CLTD5818
Name of	Kanso 2 Notch Filter (NF) Sound Processor
investigational medical device(s)	Kanso 2 Sound Processor with Forward Focus (FF)
	 CDI Tool Version 7.3.1(used in conjunction with Kanso 2 Sound Processors for programming NF and FF to device)
	Nucleus 8 (CP1110) Sound Processor (Unapproved device)
Intended use of investigational medical device(s)	The intended use and indications for use for the Kanso 2 NF Sound Processor is the same as the Kanso 2 (CP1150) Sound Processor. Intended Use: The Kanso 2 NF Sound Processor is intended to restore a level of meaningful hearing by capturing environmental acoustic sounds and/or sound from auxiliary wireless devices; processing the audio and communicating the processed audio to a compatible implant to provide electrical stimulation to the cochlea, or electrical stimulation of the auditory brainstem. While the Kanso 2 NF Sound Processor is intended to be compatible and
	can be used with Hybrid implants it is not intended to provide acoustic stimulation.
	Medical Indications for Use: The Kanso 2 NF Sound Processor requires a compatible Cochlear implant, see listed below:
	Freedom Hybrid: CI24RE (H), CI24RE (S)
	• Freedom Series Implants: CI24RE (ST), CI24RE (CA), CI24RE (CS), CI422
	• CI600 Series Implants : CI612, CI613, CI622, CI624
	CI500 Series Implants : CI512, CI513, CI522, CI532, CI551 Double Array and ABI541
	• N24 Series Implants: CI24R (CS), CI24R (CA), CI24R (ST), CI24M, CI11+11+2M, CI24MH (also known as CI6+16+2M) and ABI24M
Name and description	Kanso 2 (CP1150) Sound Processor
of comparator device/product(s)	Custom Sound Pro 6.3
	The Nucleus 8 and Kanso 2 Processing Units are intended to be used in combination with other devices as part of a hearing implant system to provide hearing sensation. The processing unit converts sounds into electrical signals, which it sends, via a coil, to an implant. The processing unit also provides power to the implant.
	When used in combination with an audio receiver, the Sound Processor also delivers sound to the ear canal in recipients with residual hearing.

Estimated recruitment period	4 weeks
Expected duration per subject	1 visit, no visit window
Number of subjects planned	9-12
Number of investigational sites planned	1 – Cochlear Limited, Sydney
Inclusion criteria	 Aged 18 years or older Post lingually deafened
	3) Implanted with the CI600 Series, CI500 Series or Freedom Series
	4) At least 6 months experience with a cochlear implant.
	 At least 3 months experience with a Nucleus 6 (CP910/920), Kanso (CP950), Kanso 2 (CP1150), or Nucleus 7 (CP1000) Sound Processor
	6) MAP Total Stimulation Rate of 7.2kHz or greater
	 Able to score 30% or more with CI alone on a monosyllabic words in quiet test
	 Willingness to participate in and to comply with all requirements of the protocol
	9) Fluent speaker in English as determined by the investigator
	10) Willing and able to provide written informed consent
Exclusion criteria	1) Additional disabilities that would prevent participation in evaluations.
	 Implant location that would result in undesirable hearing performance or discomfort with an off-the-ear sound processor, as determined by the investigator.
	 Unable or unwilling to comply with the requirements of the clinical investigation, as determined by the Investigator.
	 Investigator site personnel directly affiliated with this study and/or their immediate families; immediate family is defined as a spouse, parent, child, or sibling.
	 Cochlear employees or employees of Contract Research Organisations or contractors engaged by Cochlear for the purposes of this investigation.
	6) Currently participating or participated in another interventional clinical study/trial in the past 30 days unless (if less than 30 days) the prior investigation was Cochlear sponsored and determined by the investigator to not impact clinical findings of this investigation.
	 Implanted with other active implantable medical devices (e.g. pacemaker, defibrillator).

Objectives and Endpoints	
Primary Objective	Primary Endpoints
To evaluate the impact of NF on adult cochlear implant recipient's speech perception in quiet using an off-the-ear (OTE) Sound Processor	Paired difference in percentage CNC Words correct in quiet (50 dB) with the Kanso 2 (CP1150) Sound Processor and Kanso 2 NF Sound Processor
Secondary Objectives	Secondary Endpoints
To evaluate the performance of Forward Focus (FF) combined with standard microphone directionality on adult cochlear implant recipient's speech perception in quiet using an OTE Sound Processor	Paired difference in percentage CNC Words correct in quiet (50 dB) with the Kanso 2 (CP1150) Sound Processor and Kanso 2 Sound Processor with FF
To compare adult cochlear implant recipient's speech perception in quiet with Kanso 2 and Nucleus 8 Sound Processors	Paired difference in percentage CNC Words correct in quiet (50 dB) with the Kanso 2 (CP1150) Sound Processor and Nucleus 8 Sound Processor
Exploratory Objective	Exploratory Endpoint
To characterise the impact of NF on adult cochlear implant recipient's phoneme perception in quiet using an OTE Sound Processor	Paired difference in percentage phonemes correct in quiet (50 dB) with the Kanso 2 (CP1150) Sound Processor and Kanso 2 NF Sound Processor

3 SCHEDULE OF EVENTS

All visits can take place on the same day.

Visit Type	Screening	Visit 1	EOS
Procedures			
Written informed consent	X		
Eligibility	X		
Sentence in babble test (+15 SNR)	X*		
Demographics	X		
Hearing history	X		
Device history	X		
Medical history	X		
Device fitting		X	
Speech perception testing – Words in Quiet 50 dB		X	
Concomitant medications/therapies		X	X
Adverse events		x	X
Device deficiencies		x	Х
Device exposure		X	Х

*If required

Clinical Investigation Plan: CLTD5818

4 BACKGROUND INFORMATION AND RATIONALE

4.1 Introduction

[figure not shown]
This clinical study aims to investigate speech performance in quiet with a Kanso 2 NF Sound Processor that has modified firmware incorporating notch filters at 978Hz, 1956Hz, 2934Hz, 3912Hz compared with the commercially available Kanso 2 (CP1150). The study also investigates Nucleus 8 and and Kanso 2 with FF.

This study will build on the evidence collected in previous Nucleus 7, Nucleus 8 and Kanso 2 clinical studies (see section 4.2.2), and will inform design decisions for future Sound Processors, including decisions relating to future implant compatibility and signal processing automation.

[figure not shown]
4.2 Findings of Previous Nonclinical and Clinical Studies

4.2.1 Nonclinical Data

QMS Document Clinical Investigation Plan: CLTD5818 .

4.2.2 Clinical Data

Clinical data relevant for the current investigation fall under two main categories 1) Evidence on the development and approval of FF and 2) Evidence on previous OTE SP generation. These clinical data are summarized below:

FF Clinical Data

Signal processing strategies are designed to remove some or all competing noise, while maintaining the target speech with little or no modification. The Signal to Noise Ratio – Noise Reduction (SNR-NR) algorithm that was introduced in CP910/920 uses a single microphone or single channel input, is non-directional and performs best in steady-state background noise. The performance benefit is reduced in more modulated (non-stationary) noise such as when there are competing talkers (Dawson et al., 2011; Hersbach et al., 2012).

In contrast, FF uses two fixed-directional microphones to capture spatial information, enabling noise to be filtered based on the location of the sound source. The signal of interest is defined as originating from in front of the listener and noise as originating behind or to the sides of the listener. If SNR-NR is enabled, it can operate on the output signal from FF. The two noise reduction algorithms complement each other due to their different principles of operation. Hersbach et al. (2013) found that FF provided a significant improvement in group mean speech reception threshold compared with BEAM.

A clinical evaluation of FF performance (CRC5513), using the Nucleus 6 Sound Processor (Model CP910), revealed higher group mean speech perception scores with FF (Zoom+Strong) than with Standard, Zoom or Beam(Z) (a modification of BEAM that uses Zoom directionality) when speech was presented from the front of the listener and noise presented from the rear. Higher group mean speech recognition scores were also obtained with FF compared to Standard and Zoom algorithms with speech presented from the front of the listener and speech weighted noise (SWN) from the rear. Group mean ratings for sound quality ratings were higher with FF than with Standard, Zoom or Beam(Z). There was no significant group difference in Speech, Spatial and Qualities (SSQ) rating between FF and the comparator programs (Standard, Zoom or Beam(Z)). There was an overall preference for SCAN with FF over SCAN alone. The investigators concluded that FF is most useful at improving speech intelligibility when the competing sources are to the sides and/or rear of the listener.

In study CRC5589/CTC5614, using the Nucleus 6 Sound Processor (Model CP910), speech perception outcomes and acceptance for three different strengths of FF integrated with SCAN were compared with SCAN plus SNR-NR (N6 SCAN). Sentence recognition scores with noise in rear half noise was significantly better with all FF programs than N6 SCAN. Word recognition scores in quiet and questionnaire ratings for all FF programs were comparable to N6 SCAN. Sentence-in-noise scores obtained with speech and noise presented from the front were non-inferior to N6 SCAN for mild FF only. A decrement compared with FF Strong was found. Sentence in noise scores with speech presented to the cochlear implant side or from behind the listener with mild FF were inferior to the baseline. Based on these findings the investigators recommended that FF be introduced as a custom programme that could be selected for specific listening conditions.

Study CLTD5606 was designed to assess the effectiveness of FF for speech reception in noise compared with the Nucleus 6 SCAN (SCAN + SNR-NR). The study included twenty-five conventional

Clinical Investigation Plan: CLTD5818

CI recipients. For sentence recognition with four-talker babble from the rear, all three levels of FF (strong, medium and mild) were found to be superior to the Nucleus 6 SCAN. For SWN presented behind the listener FF Strong was demonstrated to be superior to the Nucleus 6 SCAN. When speech and either SWN or four-taker babble were co-located in front of the listener, sentence recognition with FF strong was similar to the Nucleus 6 SCAN. For CNC words in quiet FF Strong was inferior to the Nucleus 6 SCAN. The investigators concluded that acceptable performance and safety of the FF program can be anticipated for Nucleus 7 SP users in noisy environments, and the risk versus benefit profile is acceptable when FF be used in quiet environments.

The in-house study CLTD5709 investigated the effect of FF noise reduction on adult cochlear implant recipients' speech perception scores, listening effort and subjective ratings using the Nucleus 7 SP. A total of 24 subjects were enrolled in the study.

Speech perception with babble noise from the rear demonstrated that FF On was superior to FF Off (Nucleus 7 default program SCAN). Listening effort as measured via a dual-task paradigm involving both speech perception and a visual reaction time task revealed no significant difference in reaction times between FF On and FF Off, and therefore no difference in listening effort.

Questions from the Speech domain of the 'SSQ of Hearing Scale' and 3 questions from the Qualities of Hearing domain were completed by subjects at baseline and after at least 4 weeks of use with FF. The mean Speech domain results collected after 4 weeks of use were not significantly different from baseline scores.

Subjective ratings on the custom questionnaires indicated strong satisfaction, ease of use, and confidence with FF. The majority of respondents found the FF controls within the Nucleus Smart App as very easy to use and half of the respondents wanted FF on their own processor.

Clinical Data for OTE Sound Processors

The main relevant study with an OTE Sound Processor is the CLTD5754 study, the primary objective of this study was to determine the feasibility of FF in an OTE configuration and the secondary objective was to collect formative usability information with prototype and early design versions of the Kanso 2 (CP1150) Sound Processor.

Twenty-two adult subjects underwent speech perception testing using Australian Speech Test In Noise (AuSTIN) adaptive sentences presented from the front with 4 talker babble noise from 90,180 & 270 degrees to the subject (S0N3). AuSTIN Speech Reception Threshold (SRT) data comparing FF ON and FF OFF demonstrated superiority with FF ON (P=0.002, paired t-test).

The implementation of FF in the CLTD5754 included the fixed microphone directionality Zoom and no automation. This evidence supported the approval of FF with the Kanso 2 Sound Processor.

4.3 Study Rationale

This investigation is planned to evaluate the performance of signal processing additions and features that may be new to a future version of the OTE Sound Processor. This study will build on the evidence previously collected on OTE and behind-the-ear (BTE) Sound Processors and will support the design goals for access to the same sound processing algorithms across future OTE and BTE variants, including evidence required on the automation of FF and future implant compatibility. This

study is intended to assess the clinical impact of the design choices made to achieve these future design goals, including:

- **Future implant compatibility:** As a result of the proximity of the split link RF coil to the acoustic electronics, noise has been measured on the bench with an OTE coupled to a future implant design. This study will investigate whether the proposed notch filters have an impact on performance in quiet compared to a current commercially available OTE (Kanso 2).
- Automation of ForwardFocus on an OTE Sound Processor: Previous BTE studies have shown a small decrement in speech perception in quiet with ForwardFocus compared to no ForwardFocus (D1376556), however parameter changes and automation have been implemented to resolve this issue, including the reduction in strength of FF and the inclusion of the standard directionality (std) in the 'Quiet' class. This study will assess whether FF (moderate)+standard directionality provides acceptable performance in quiet compared to the current commercially available Kanso 2 with FF.
- Kanso 3 vs Nucleus 8 Claim The study also aims to provide confirmatory evidence on the comparability of OTE and BTE Sound Processors in quiet.

A more detailed description of the test conditions and rationale for their inclusion is available in Table 2.

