5.2 Identity and Description of the Comparator

Kanso 2 (CP1150) Sound Processor:

Kanso (CP1150) Sound Processor is the commercially available predecessor device to the investigational Kanso 2 NF Sound Processor. Kanso 2 will be used as the comparator device for speech perception testing in quiet (CNC words) for both the NF and FF comparisons.

Nucleus 8 (CP1110) Sound Processor:

Nucleus 8 is an unapproved BTE Sound Processor. The Nucleus 8 is considered a suitable comparator for the OTE vs BTE comparison (secondary endpoint 2) because of the similarities to the commercially available predicate Nucleus 7 Sound Processor, and because Nucleus 8 includes signal processing features aligned with the next generation of OTE Sound Processor.

Comparator	Endpoint	Justification
Kanso 2 (CP1150) Sound Processor	Primary Endpoints Paired difference in percentage CNC Words correct in quiet (50 dB) with the Kanso 2 Sound Processor and Kanso 2 NF Sound Processor	Input processing: Standard microphone directionality + SNR-NR + subject's own MAP and ADRO/ASC preference Standard microphone directionality has been chosen to be consistent with the microphone directionality that SCAN+ selects in a quiet setting, and because the impact of the notch filters have the greatest potential for impact on speech in quiet.
Kanso 2 (CP1150) Sound Processor	Secondary Endpoints Paired difference in percentage CNC Words correct in quiet (50 dB) with the Kanso 2 Sound Processor and Kanso 2 Sound Processor with FF	Input processing: Standard microphone directionality + SNR-NR + subject's own MAP and Adaptive Dynamic Range Optimisation Autosensitivity (ADRO/ASC) preference Standard microphone directionality has been chosen to be consistent with the microphone directionality that SCAN+ selects in a quiet setting, and because the research question includes the performance of FF in a quiet scenario.
Nucleus 8 (CP1110) Sound Processor	Secondary Endpoints Paired difference in percentage CNC Words correct in quiet (50 dB) with the Kanso 2 Sound Processor and Nucleus 8 Sound Processor	Input processing: Standard microphone directionality + SNR-NR + subject's own MAP and ADRO/ASC preference Standard microphone directionality has been chosen to be consistent with the microphone directionality that SCAN+ selects in a quiet setting

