6.2 Secondary Objectives

- To evaluate the performance of FF combined with standard microphone directionality on adult cochlear implant recipient's speech perception in quiet using an OTE Sound Processor.
- To compare adult cochlear implant recipient's speech perception in quiet with Kanso 2 and Nucleus 8 Sound Processors

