7.2.3 Number of Subjects Required

The total number of subjects to be enrolled in the study to meet sample size calculation requirements is 12, which includes 3 additional subjects to account for an expected dropout rate of 25%.

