- Case Report Form Completion

Device Fitting

Prior to assessing speech perception in quiet, the test Sound Processors will be loaded according to the input processing settings identified in Table 4.

ADRO is the adaptive dynamic range optimisation processing setting, and ASC is the auto sensitivity processing setting, both of which will be enabled or disabled in the test Sound Processors according to each subject's preferred settings on their own MAP; if the study subject uses and prefers ADRO and ASC in their own Sound Processor, then these setting will be enabled in the study Sound Processor.

SNR-NR is a single channel noise reduction algorithm and directionality refers to the microphone directionality that will be enabled. These signal processing settings will be enabled/disabled via the fitting software CDI Tool and Custom Sound Pro.

Speech perception in quiet test

In booth speech perception testing will be conducted using the input processing combinations and hardware listed in Table 4. The order of testing will be conducted according to the counterbalancing outlined in Section **Error! Reference source not found.**

	Notch filters	WNR	SNR-NR	Directionality	ADRO & ASC	FF
Kanso 2		~	~	Std	As per user preference	
Kanso 2 NF	×	✓	~	Std	As per user preference	
Nucleus 8		~	~	Std	As per user preference	
Kanso 2 FF		×	~	Std	As per user preference	✓(Mild)

Table 4. Speech in Quiet test conditions.

Wind Noise Reduction (WNR); Signal to Noise Ratio- Noise Reduction (SNR-NR); adaptive dynamic range optimisa ion (ADRO); auto sensi ivity (ASC); ForwardFocus (FF)

All subjects will be tested in the unilateral condition and each subject will have their contralateral ear (non-test ear) blocked with an ear plug for all test conditions. Subjects with bilateral implants that meet the inclusion criteria will be tested using the subject's preferred ear or if the preferred ear is not known then the first implanted ear will be used as the test-ear.

The subject will be positioned so that the middle-point between the two ears is centred at the reference point of the sound field. The loudspeaker should be positioned at the same height as the middle-point of the two ears.

The AuSTIN software will be used to present the test material. The investigator, or suitably qualified delegate will use the software to select:

- CNC word test
- 50 dB SPL presentation level
- Signal from in front (0 degrees)
- 2 lists of 50 words each

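### Does the Kanso 3 label in CIP 4.3 attach the Nucleus 8 comparison to a device the study does not test?

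*Protocol*

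**What the plan says.** CIP 4.3 lists three design goals. The third is "Kanso 3 vs Nucleus 8 Claim The study also aims to provide confirmatory evidence on the comparability of OTE and BTE Sound Processors", in quiet. The section then closes: "A more detailed description of the test conditions and rationale for their inclusion is available in Table 2".

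Table 2 (CIP 5.2) defines the Nucleus 8 endpoint as "Paired difference in percentage CNC Words correct in quiet (50 dB) with the Kanso 2 Sound Processor and Nucleus 8 Sound Processor". The text above it gives the purpose: "The Nucleus 8 is considered a suitable comparator for the OTE vs BTE comparison (secondary endpoint 2"). The secondary objective in CIP 6.2 is to compare "speech perception in quiet with Kanso 2 and Nucleus 8 Sound Processors". CIP 9.2.2 and 9.3.2, and SAP 2.2 and 3.1.3, keep the same pair, with Kanso 2 as treatment and Nucleus 8 as control. CIP 9.3 and SAP 3 specify Kanso 2 without notch filters. The conditions listed in CIP 7.3 under "Table 4. Speech in Quiet test conditions" are Kanso 2, Kanso 2 NF, Nucleus 8 and Kanso 2 FF.

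**The concern.** CIP 5.1.1 describes Kanso 2 as the current commercial off-the-ear processor. Kanso 3 therefore reads as a later product, and a heading that speaks of a claim for it reads as an intended use of the result. The arm compared with Nucleus 8 carries neither of the additions discussed in CIP 4.3: it has no notch filters, and ForwardFocus is switched on only in the separate Kanso 2 FF condition. No visible text explains why a Kanso 2 result would carry over to Kanso 3.

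What would be at stake is the scope of the second secondary conclusion. A reader who relied on the heading could cite a non-inferiority result for a device name that was never tested, or for a configuration with notch filters that does not enter that comparison.

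**Working it through.** **1. Which device does each place name?**

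| Place | Off-the-ear device set against Nucleus 8 |
|---|---|
| CIP 4.3, label of third bullet | Kanso 3 |
| CIP 4.3, sentence under the label | none named; off-the-ear versus behind-the-ear in general |
| CIP synopsis, 5.2 (Table 2), 6.2, 9.2.2, 9.3.2 | Kanso 2 |
| CIP 9.3 (comparison list) | Kanso 2, no notch filters |
| CIP 7.2.7 (Table 3), 7.3 (Table 4) | Kanso 2 (Kanso 2 NF and Kanso 2 with FF are separate conditions) |
| SAP 1.2, 2.2, 2.3, 3.1.3 | Kanso 2 |
| SAP 3 (decision rule) | Kanso 2, no notch filters |

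Kanso 3 appears in 0 of 4 test conditions and 0 of 3 hypothesis tests. The only place that uses the name is the label.

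**2. Is the conclusion already limited to the tested device?** SAP 3 says which processor is declared non-inferior when the lower confidence limit is above -10%. For the second secondary endpoint that processor is Kanso 2 without notch filters, against the control processor. The wording about standard omni in that sentence is clumsy, but the device is not in doubt. A further scope sentence in CIP 9.7 or SAP 8.1 would mostly repeat it.

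**3. Does any figure depend on the label?** Inputs from CIP 9.4 and 9.6: margin 10 points, SD of paired differences 7.5 points, one-sided alpha 0.025, target power 0.90. The true difference is not stated; I take it as 0.

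Power = P(T > t(0.975, n-1)), where T is noncentral t with n-1 degrees of freedom and noncentrality 10 / (7.5/√n).

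- n = 8: noncentrality 10/(7.5/√8) = 3.77, power 0.896.
- n = 9: noncentrality 10/(7.5/3) = 4.00, power 0.937.
- n = 12: noncentrality 10/(7.5/√12) = 4.62, power 0.987.

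Nine is the smallest n that reaches 0.90, so the plan's figure reproduces. Enrolment is 9/(1 - 0.25) = 12, which agrees with CIP 7.2.3: "3 additional subjects to account for an expected dropout rate of 25" per cent.

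The 7.5 comes from off-the-ear studies, and the documents give no SD for an off-the-ear versus behind-the-ear difference. With assumed values, power at n = 9 and n = 12 is 0.83 and 0.94 for SD 9, and 0.70 and 0.84 for SD 10.6 (7.5 × √2). That range reflects uncertainty about the SD. The device name does not enter the formula, so relabelling the bullet leaves every value as it is.

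**The case for a change.** The strongest case for acting is that this is more than a typing error. The label speaks of a claim and of confirmatory evidence, the device it names is undefined in the visible text, and neither CIP 9.6 and 9.7 nor SAP 8.1 says how far the Nucleus 8 conclusion reaches. The remark in CIP 5.2 that Nucleus 8 shares features with the next off-the-ear generation justifies the control; it does not make Kanso 2 a stand-in for a later device. Rewording one label would cost almost nothing.

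Part of this stands. The label does not match the tested device, and no bridging argument is visible. One could sit in material missing from this copy (the figures of CIP 4.1, the text of CIP 4.2.1), but the tested device would still be Kanso 2.

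The rest carries less weight:

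- CIP 4.1 and 4.3 present the whole study as informing future processors, so a label that looks ahead to a future product fits the section. A reader would be misled only by passing over the sentence beneath it, the pointer to Table 2, and the objective, endpoint and hypothesis.
- The limit on scope missing from SAP 8.1 is in SAP 3.
- One could add an estimate of Kanso 2 NF minus Nucleus 8, in case the future device carries the filters. The documents do not say that it will. CIP 4.3 links the filters to a compatibility problem: "noise has been measured on the bench with an OTE coupled to a future implant design". Such a contrast would also mix form factor with filter effect, so it would not answer the off-the-ear versus behind-the-ear question more clearly.

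The generic decision sentence at the end of CIP 9.3 has its own naming slip (it refers to Nucleus 8 and Nucleus 7). SAP 3 replaces it with the correct processors, and it has no bearing on the Kanso 3 label.

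**Conclusion.** The concern does not call for a change. One label in the rationale names Kanso 3; everything that governs testing, analysis and conclusion names Kanso 2. The planned contrast suits the purpose given in CIP 5.2, and SAP 3 already confines the conclusion to Kanso 2 without notch filters. The effect on the test, decision rule, primary endpoint and sample size is nil: 9 evaluable and 12 enrolled subjects reproduce under the plan's inputs and a true difference of 0.

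This rests on the result being reported under the device names in SAP 3, as the plan requires. A later statement about Kanso 3 would need its own justification for extrapolating from Kanso 2, and that matter belongs to the document making the statement. If the protocol is reissued for another reason, the label could be tidied as an editorial matter.
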